10.2. Epidermis thickness (only for PsO)

10.2.1. Endpoint / Variables

Epidermal thickness is measured by making 35 transect measurements across the entire diameter of the epidermis. The values are in the following SI dataset: MI.

Parameter	Endpoint	Derivation	HV (DTH)	PsO
Epidermis	Epidermis thickness	Mean of the 35 measurements	N	Υ
thickness	(µm)			(epidermis)

10.2.2. Summary Measure

Absolute, change from baseline and percent change from baseline are of interest for PsO.

Data will be available at baseline and Day 29 (for PsO).

10.2.3. Population of Interest

The primary pharmacodynamics and biomarker analyses will be based on the Safety population, unless otherwise specified.

10.2.4. Statistical Methods

Details of the planned displays are provided in Appendix 9 and will be based on GSK data standards and statistical principles.

Unless otherwise specified, endpoints / variables defined in Section 10.2.1 will be summarised using descriptive statistics, graphically presented (where appropriate) and listed.

10.2.4.1. Statistical Methodology Specification

Endpoint / Variables

- For epidermis only (PsO), change from baseline in
 - Epidermis thickness (µm)

Model Specification

- Endpoints will be statistically analysed using an ANCOVA model.
- Terms fitted in the model will include: Treatment and baseline

Model Results Presentation

- Summary table of the LS means and 95% CI for CFB (by treatment)
- [No plot as only 1 post-dose assessment]

10.3. Other PD parameters

10.3.1. Endpoint / Variables

The following endpoints are of interest (SI dataset: BIOMARK):

- s-LAG3 parameters no derivation is needed
- Flow cytometry 6 key parameters only described below:

Marker code	Marker	Type (BITESTCD)	Unit (BISTRESU)
CDX226	CD45+ CD3- CD19+	Concentration	CELLS/UL
CDX258	CD45+ CD3+ CD69+	Concentration	CELLS/UL
CDX444	CD4+CD45RA+1B4+	Number of events	COUNT
CDX445	CD4+CD45RA+J11L1+	Number of events	COUNT
CDX446	CD4+CD45RA-1B4+	Number of events	COUNT
CDX447	CD4+CD45RA-J11L1+	Number of events	COUNT

For 4 of these endpoints (CDX444, CDX445, CDX446, CDX447), the derivation below should be applied (same derivation as for PK analyses):

The count at each time point is the difference: BISTRESN value in the row with BIEXPS = "Stained Sample - T cell markers including J11 and 1B4" - BISTRESN value in the row with BIEXPS = 'LAG3 FMO Control - T cell markers excluding J11 and 1B4'

10.3.2. Summary Measure

- S-LAG3: absolute, change from baseline for total soluble LAG3 concentrations
- Flow cytometry: absolute, change from baseline and percent of baseline, where the percent of baseline is: 100 * post-dose visit value

 Recelline

10.3.3. Population of Interest

The primary pharmacodynamics and biomarker analyses will be based on the Safety population, unless otherwise specified.

10.3.4. Statistical Methods

Details of the planned displays are provided in Appendix 9 and will be based on GSK data standards and statistical principles.

Unless otherwise specified, endpoints / variables defined in Section 10.3.1 will be summarised using descriptive statistics, graphically presented and listed.

10.4. Transcriptomics (biopsy and blood)

10.4.1. Endpoint / Variables

The following endpoints are of interest:

- Blood transcriptomics (HV, PSO):
 - 1. 2 genes: LAG-3 long, LAG-3 short
 - 2. 2 housekeeping genes: POL2RG, POL2RJ
- Biopsy (skin) transcriptomics (PSO only)
 - 1. 18 genes (including the 2 common genes for blood transcriptomics)

LAG-3 Long	LAG-3 Long Gene mRNA Expression
LAG-3 short	LAG-3 short Gene mRNA Expression
IL-17A	IL-17A Gene mRNA Expression
IL-17F	IL-17F Gene mRNA Expression
IL-22	IL-22 Gene mRNA Expression
IL-23	IL-23a Gene mRNA Expression
IFNg	IFNg Gene mRNA Expression
IL-12A	IL-12A Gene mRNA Expression
IL-10	IL-10 Gene mRNA Expression
FOXP3	FOXP3 Gene mRNA Expression
S100A12	S100A12 Gene mRNA Expression
Ki67	Ki67 Gene mRNA Expression

K16	K16 Gene mRNA Expression
CD3g	CD3g Gene mRNA Expression
TSPAN8	TSPAN8 Gene mRNA Expression
CLDN8	CLDN8 Gene mRNA Expression
CCL27	CCL27 Gene mRNA Expression
CDHR1	CDHR1 Gene mRNA Expression

2. 2 housekeeping genes (same as for blood transcriptomics): POL2RG, POL2RJ

Data available (SI dataset: PF – pharmacogenomics findings):

- Analyte (Collected Specimen Type code): skin or blood
- Gene (Genetic Region of Interest code)
- Type of values (Pharmacogenomics Test code)
 - Cycle times (Ct) 3 per subject
 - Mean of the Cts
 - Delta Ct
 - Delta Delta Ct
 - Fold change

No derivation is needed by S&P as provided by the vendor.

10.4.2. Summary Measure

For all endpoints above:

- Delta delta Ct baseline versus post-baseline visit
- Fold change from baseline to post-baseline visit: always strictly positive (=2^ delta delta Ct)

Post-baseline visits:

- HV (DTH and non DTH): Day 2 (Blood only)
- PsO: Day 2 (blood), Day 15 (skin, only cohort 7, removed for cohorts 8 and 9 in amendment 8), Day 29 (skin)

10.4.3. Population of Interest

The transcriptomics analyses will be based on the Safety population, unless otherwise specified.

10.4.4. Statistical Methods

Details of the planned displays are provided in Appendix 9 and will be based on GSK data standards and statistical principles.

Unless otherwise specified, endpoints / variables will be summarised using descriptive statistics, graphically presented and listed.

11. PHARMACOKINETIC / PHARMACODYNAMIC ANALYSES

The PK/PD analyses will be based on the PK population, unless otherwise specified.

The primary goal of this analysis is to characterise the PK/PD relationship of GSK2831781 administered IV in healthy subjects and psoriasis patients. The influence of subject demographics and baseline characteristics will be investigated.

A summary of the planned population PK/PD analyses are outlined below:

[figure not shown]
- Drug GSK2831781 plasma concentration and corresponding receptor occupancy data will be subjected to nonlinear mixed effects modelling using the program NONMEM to develop a population PK/PD model.
- To support this analysis a PK/PD dataset will be generated. The details for the dataset specifications are provided in Appendix 7.
- Detailed PK/PD methodology is presented in Appendix 7.

A PK/PD report will be produced by CPMS, and will be included as an appendix to the CSR.

12. IMMUNOGENICITY ANALYSES

The immunogenicity analyses will be based on the Safety population, unless otherwise specified.

Information from the screening assay contributes to the number at risk for the calculation of % positive. The calculation of 'n' is displayed in the diagram below as a guide.

There are no planned statistical analyses.

Details of the planned displays are provided in Appendix 9 and will be based on GSK data standards and statistical principles.

13. BAYESIAN ANALYSES (PART B)

To aid decision making, the following posterior probabilities, will be evaluated:

For **PASI/PLSS**:

- Difference of interest = Difference (active placebo) in % CFB,
- Probabilities of interest

P(difference < 0) $P(difference \le 10\%)$ $P(difference \le 20\%)$ $P(difference \le 30\%)$ $P(difference \le 40\%)$

For **total LAG3 cells** for the epidermis and dermis:

- Difference of interest = Difference (active placebo) in % CFB
- Probabilities of interest

P(difference < 0) $P(difference \le 30\%)$

For Ki67 and epidermis thickness:

- Difference of interest = Difference (active placebo) in CFB
- Probabilities of interest

P(difference < 0)

The active and placebo treatment groups mentioned above are defined as follows:

- Subjects in the active group are defined as psoriasis patients that received the doses 1.5mg/kg and 5mg/kg (pooled cohorts 8 and 9). In total, 12 subjects are on active.
- Subjects in the placebo group are defined as psoriasis patients that received placebo in cohorts 7-9. In total, 9 subjects are on placebo.

The propobabilities described above may also be calculated for each dose (i.e. 1.5mg/kg versus placebo and 5mg/kg versus placebo).

For PASI and PLSS, the change from baseline to lowest non-missing post-baseline response will be derived for each subject, considering all their available assessments out to day 85. The Bayesian analyses will be conducted for these derived endpoints to provide an overall summary, as oppose to a distinct assessment at each timepoint. For the other endpoints changes from baseline to day 29 will be assessed.

Changes from baseline in each parameter will be analysed using a linear regression, including treatment (active and control as defined above) and baseline score:

 $Y_i \sim \text{Normal}(\mu_i, \text{precision} = \tau)$ $\mu_i = \beta_0 + \beta_1 Base_i + \beta_2 Treatment_i$ Where Y_i is the observed change from baseline response for each subject as defined above.

Non-informative conjugate prior distributions are assigned to the unknown parameters:

- Intercept and slope coefficients: β_0 , β_1 , $\beta_2 \sim \text{Normal}(0, \text{precision} = 10^{-3})$ Sensitivity analysis with precion=0.1
- Between-subject precision (1/variance): $\tau \sim$ Gamma (shape = 0.001, rate = 0.001), i.e. $E(\tau) = 1$

One MCMC chain will be run. At least 10 000 iterations will be used for the burn-in period as well as for the inference. The number of iterations may be increased to ensure that the ratio MCSE/SD for all the parameters in the model is ≤ 0.01 .

Visual inspection of MCMC output (including, but not limited to, trace and autocorrelation plots) will be used to assess the convergence.

The posteriror distribution of the difference in % CFB will be generated as β_2 / $mean_Base$. The later is modelled as a normal distribution and assumed that there is no treatment difference for baseline values before treatment: $Base_i \sim Normal(mean_Base,$ precision = τ_Base). Non-informative conjugate prior distributions are assigned to the unknown parameters:

- mean Base \sim Normal(0, precision = 10^{-3})
- Between-subject precision (1/variance): τ _Base ~ Gamma (shape = 0.001, rate = 0.001), i.e. $E(\tau) = 1$

The posterior probabilities that the difference in %CFB or CFB is above a pre-defined threshold will be calculated based on the above posterior distributions.

Results will be displayed in a table, with the number of subjects in each group, active and control.

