3. STUDY DESIGN

3.1. Study Schematic

3.1.1. PPD injection sites

Day 1

All injection sites should be 4 cm apart from each other and from Day 1 injection sites

Study Design Summary 3.1.2.

Table 1 Dose escalation/Cohort Structure and Safety review periods

Planned Doses	Number of subjects (active:placebo)	Safety Follow-up period to progress to next subjects/cohorts	PPD DTH Challenge if Healthy volunteer/ Biopsy if patient	Follow-up and end of exclusion of systemic immunosuppressives
Healthy Volunt	teers			
0.0003mg/kg	1:1	1:1 1:1 wait 28 days post- dose No DTH	No DTH	Day 29 ± 1 day (28 days post-dosing)
0.0015mg/kg				Day 43 ± 1 day (42 days post-dosing)
0.0075mg/kg	6:2	1:1 wait 48 hours post-dose	No DTH	Day 85 ± 2 days (84 days post-dosing)
0.04mg/kg		5:1 wait 28 days post- dose		Day 147 ± 3 days (146 days post-dosing)
0.15mg/kg	6:6	1:1 wait 48 hours post-dose 5:5 wait 28 days post- dose	DTH	Day 219 ± 7 days (190 days post-dosing)
0.15mg/kg*	6:2	1:1 wait 48 hours post-dose 5:1 wait 28 days post- dose	No DTH	Day 189 ± 7 days (190 days post-dosing)
Note: Cohort wi	th a DTH starts dosing	g on Day 29	1	
*Note: No DTH without pre-exis		.15mg/kg is in subjects wi	th pre-existing ADA. A	Il previous cohorts are in subjects
Maximum dose	for healthy volunteers	may change based on e	merging exposure (See	e Section 3.2.1)
Psoriasis Patie	ents (Pre-existing AD	A- and ADA +)		
0.5mg/kg	6:3(ADA-ve 4:2 ADA+ve: 2:1)	1:1 ADA-ve wait 48 hours post-dose 5:2 wait 28 days post- dose*	Biopsy	230 days post-dosing ± 7† days
1.5mg/kg	6:3	Sentinel 1:1 - wait 48 hours post-dose 5:2 - then wait 28	Biopsy	183 days post-dosing ± 7† days (prior to Amendment 10 was 270 days)

hours post-dose 5:2 - then wait 28 days post-dose*

Planned Doses	Number of subjects (active:placebo)	Safety Follow-up period to progress to next subjects/cohorts	PPD DTH Challenge if Healthy volunteer/ Biopsy if patient	Follow-up and end of exclusion of systemic immunosuppressives
5mg/kg	6:3	Sentinel 1:1 - wait 48 hours post-dose 5:2	Biopsy	183 days post-dosing ± 7† days (prior to Amendment 10 was 300 days)

Note: All follow-up days may be increased or decreased during the study based on emerging data (See Section 3.3.1)

*Note: Progression to the next psoriasis cohort will be based on safety data and clinical measures of response at 28 days post-dose for a minimum of 8 out 9 subjects plus a minimum of 72 hours post-dose for all subjects.

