- Removal of the stratification of psoriasis patients according to their pre-existing antidrug antibody (ADA) status, and to recruit "all-comers" into the remainder of Cohort 8 and into Cohort 9. The justification is based upon de-escalation of concerns regarding the theoretical impact of pre-existing ADAs following the review of Cohort 7 data and their substantially lower frequency in the patient population than predicted (patient pool has been screened to exhaustion). None of the events listed here have been observed following a single 0.5 mg/kg intravenous infusion: serious adverse event, immediate hypersensitivity, infusion reaction, cytokine release syndrome, type III hypersensitivity any other safety concern or any impact of ADA on pharmacokinetics. Importantly, enrolling patients at higher doses (1.5 or 5.0 mg/kg) is no longer considered necessary to test for overt risk of immediate hypersensitivity, infusion reactions, cytokine release or type III hypersensitivity.
- 2. Introduce the possibility of additional Interim Analyses to enable internal development decisions (See Section 9.3.1)
- 3. Consolidation of previously enacted File Notes since Protocol Amendment #8 (See Time and Events Table 9 and Table 10).
 - a. File Note [12th Dec 2016] Following the blinded review of Cohort 7 data, the following changes (permitted by the protocol) were deemed necessary to both bridge the anticipated shortfall in the critical portion of the kinetic profile and to secure the utility of this study to inform the next steps in rational clinical development (e.g. definition of the dose regimen):-
 - Adjustment of the pharmacokinetic sampling schedule (additional sample Days 29 and 57).
 - Introduction of one new (different) visit per each Cohort 8 [Day 36] and Cohort 9 [Day 71] to enable capture of important pharmacokinetic time points.
 - Adjustment to the timing of immunophenotyping (chip cytometry).
 - Introduction of psoriasis efficacy assessments at Day 85 (non-invasive). The overall blood volume (484 mL) remains below that approved (600 mL).

- b. File Note [7th Nov 2016] Downward adjustment of the overall blood volume (minus 44 mL) as a result of the following:

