Interim 2	 Formal unblinded interim analysis will be conducted during part B. The PASI and PLSS will be evaluated when the last psoriasis patient in cohort 9 has completed D43 visit, and the full interim 2 evaluation will be conducted after all patients have completed their day 85 visit. Data for healthy volunteers and psoriasis patients will be included. 					
	 The purpose of this interim analysis is to provide the project team and GSK stakeholders with key data to inform internal decision making, in order to plan future studies within the clinical development for the asset. 					
	There are no planned implications for the conduct of the study.					
	 Appropriate data summaries will be at the subject and treatment group level for key endpoints of interest and the circulation of results will be restricted to selected members of the project team and key GSK stakeholders. Results or discussions will not be circulated to blinded staff involved in the conduct of the study at the sites. 					

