8.3.2. Summary Measure

 Absolute PASI scores, change from baseline and percent change from baseline in PASI scores over time • Proportion of subjects who achieve ≥50% improvement from baseline in PASI score (PASI 50), at each post-baseline visit Proportion of subjects who achieve ≥75% improvement from baseline in PASI score (PASI 75) at each post-baseline visit. If the PASI score is missing, set PASI 50 or 70 to missing.

Note: Day 85 was not assessed for 0.5mg/Kg dosing cohort (cohort 7).

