14.9.3. Deliverables

Following review of the IA2 and IA W2 outputs and finalisation of the database, the final list of outputs to be re-run at SAC will be reviewed.

Delivery	Description
IA1	Interim Analysis 1 Statistical Analysis Complete
IA2 EFF Interim Analysis 2 Statistical Analysis Complete for Efficacy endpoints	
IA2 Interim Analysis 2 Statistical Analysis Complete	
IA2 W2 Interim Analysis 2 Wave 2 Statistical Analysis Complete	
SAC	Final Statistical Analysis Complete

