2.12.	Safety	TE4	Summary of PGA responses by visit for psoriasis patients	Frequency count (categorical variable)	IA2 EFF
Endpoi	nts for go/no g	o decisions			
2.13.	Safety		Bayesian analyses of key endpoints	See Section 13 IA2 EFF: PASI and PLSS IA2: total LAG3 cells, Ki67, epidermis thickness Need to add SAS log + CV plots	IA2 EFF IA2

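### SAP 13 calls its Bayesian priors non-informative, but they are fixed in raw units and can distort the go/no-go probabilities for biopsy endpoints with a large raw SD

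*SAP*

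**What the plan says.** SAP 13 fits a normal linear regression of change from baseline on an intercept (beta0), baseline (beta1) and treatment (beta2). Active is cohorts 8 and 9 pooled (12 patients). For placebo, "Subjects in the placebo group are defined as psoriasis patients that received placebo in cohorts 7-9" (9 patients). Per-dose runs are optional.

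Every coefficient has a Normal(0, precision 10^-3) prior, described as non-informative and used for all endpoints. The one sensitivity prior has precision 0.1. For PASI, PLSS and LAG-3+ the reported quantity is the difference in % change, computed as beta2 divided by mean_Base, and mean_Base has the same Normal(0, precision 10^-3) prior. For Ki67 and epidermal thickness the only listed output is P(difference<0) on the raw change. No rescaling is described.

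For the clinical scores, "For PASI and PLSS, the change from baseline to lowest non-missing post-baseline response will be derived for each subject", using all available assessments to Day 85. SAP 8.3.2 notes: "Day 85 was not assessed for 0.5mg/Kg dosing cohort (cohort 7". The Amendment 9 log in Protocol Appendix 6 explains why: "Introduction of psoriasis efficacy assessments at Day 85 (non-invasive" followed the review of cohort 7.

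The results form Table 2.13 (SAP 14.9.5), under the heading for go/no-go endpoints, with this delivery: "IA2 EFF: PASI and PLSS IA2: total LAG3 cells, Ki67, epidermis thickness".

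**The concern.** A normal prior with a fixed SD is vague only relative to the scale of the outcome. Here one SD serves PLSS points, PASI points, cell counts summed over three to five high power fields (SAP 10.1.1) and thickness in µm (SAP 10.2.1). If the sampling error of an effect is comparable with 31.6 units, the prior acts as real evidence that the effect is near zero. The probabilities then do not have the property the SAP claims for them.

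The sensitivity prior does not help. It is tighter, so it can reveal that the prior matters but cannot show the non-informative answer.

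At stake is the internal development decision. The ANCOVA is prior-free but reports LS means by treatment (SAP 10.1.4.1, 10.2.4.1), not the pooled active-minus-placebo contrast, so it does not replace this table.

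**Working it through.** **The plan's own figures.** 6+6 = 12 active and 3×3 = 9 placebo; E(tau) = 0.001/0.001 = 1. The PLSS half-width in Protocol 9.2.1 is t(5, 0.975)×24.8/√6 = 26.0%, as stated. All reproduce.

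**Prior SDs.** 1/√0.001 = 31.6 raw units. Sensitivity prior: 1/√0.1 = 3.16.

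**Weight left on the data for beta2** (zero intercept, residual SD taken as known): w = 1000/(1000 + SE²), with SE² = SD²×(1/12 + 1/9) = 0.1944×SD². The residual SDs are assumptions, because the documents give none for the biopsy endpoints.

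| Residual SD | w, precision 10^-3 | w, precision 0.1 |
|---|---|---|
| 5 (PASI/PLSS range) | 0.995 | 0.673 |
| 25 | 0.892 | 0.076 |
| 50 | 0.673 | 0.020 |
| 100 | 0.340 | 0.005 |

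Half the effect is lost at SD = √(1000/0.1944) = 71.7. For 6 v 9 it is √(1000/0.2778) = 60.0.

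**Gibbs sampling of the SAP model**, 12 v 9, least-squares effect fixed at 2 SE, zero intercept, residual SD 25/50/100:
- Precision 10^-3: about 88/68/35% of the effect kept; P(difference<0) 0.96/0.95/0.88.
- Precision 10^-6: over 99% kept; P = 0.97 throughout.
- Precision 0.1: P = 0.71–0.73/0.61–0.62/0.56.

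**Intercept.** It has the same prior, so a large intercept is also pulled to zero and part of the misfit moves into beta2. At +2.5 SD, P falls to about 0.80–0.89 (SD 50) and 0.60–0.77 (SD 100). At −2.5 SD and SD 50, 79–90% is kept and P is 0.96–0.97. These ranges are indicative. They move with the assumed baseline mean and slope, and other settings gave P as low as 0.49 (+2.5 SD, SD 100) or as high as 0.99 (−2.5 SD, SD 50).

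**Denominator of the LAG-3+ % change.** Assume baseline mean 200, SD 100, n = 21. With the SD known, the weight is 1000/(1000 + 100²/21) = 0.68. The variance is estimated too, and it grows as the mean is pulled away from the data, so the sampler settles lower: mean_Base is about 102, half its true value. Net effect on the percentage:
- Residual SD 60: w = 1000/(1000 + 700) = 0.588, and 0.588×200/102 = 1.15. The effect is overstated: a 2-SE reduction of 26.5% becomes about 31%, and the probability of at least a 30% reduction rises from 0.40 to about 0.51. (I read the SAP's 30% threshold as a reduction.)
- Residual SD 100: 0.35×200/102 = 0.69. The effect is understated.

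**Secondary: visits in the best score.** For k equally correlated visits the expected minimum is −SD×√(1−ρ)×c_k, with c_3 = 0.8463 and c_4 = 1.0294. Take SD 24.8% (given for PLSS, also applied to PASI) and assumed ρ of 0.3–0.7. One extra visit is then worth 24.8×√(1−ρ)×0.1831 = 3.8 to 2.5 points. By schedule 3 of 9 placebo and 0 of 12 active patients lack Day 85, so the pooled bias is one third of that, 1.3 to 0.8 points in favour of active. This is 0.08–0.15 SE, with null P(difference<0) of 0.52–0.54.

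That is with Day 85 complete. Table 2.13 lists PASI/PLSS only for IA2 EFF, and "The PASI and PLSS will be evaluated when the last psoriasis patient in cohort 9 has completed D43 visit". Cohort 9 could start once cohort 8 had "clinical measures of response at 28 days post-dose for a minimum of 8 out 9 subjects plus a minimum of 72 hours post-dose" for all (note to Protocol Table 1). At that fastest pace the first cohort 8 patient is at about Day 75–80 at the cut, nobody has Day 85, and the bias is zero. A later repeat is left open: "the final list of outputs to be re-run at SAC will be reviewed".

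**The case against.** The strongest reply is that the size rests wholly on assumed SDs. That stands. Thickness in µm is plausibly large from its unit alone, and LAG-3+ totals may be. Ki67 is labelled per mm² but derived as cells divided by number of fields (SAP 10.1.1), so nothing shows that it is on a large scale.

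A reader might infer that the prior always works against the drug. The documents do not support that. The pull on beta2 depends on the intercept, and mean_Base carries the same prior, so the LAG-3+ 30% probability can err in favour of active.

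A reader might also infer that the missing Day 85 visit tilts the go/no-go table. It does not in any material way: the pooled bias is about a tenth of an SE and may be zero at the planned cut. The larger per-dose figures (up to 2.5 points for 1.5 mg/kg) need optional runs and a cut where all of cohort 8 and none of cohort 9 has Day 85. For PLSS the missing visit is inferred from the amendment log. The MMRM already gives PASI and index-plaque PLSS differences by visit, and Day 85 was added on purpose, so dropping it from the planned endpoint is a trade-off.

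Finally, SAP 3.1 plans no effect on study conduct and no decision cut-off is set, so the stakes are internal.

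**Conclusion.** The point holds for the priors. The label non-informative is wrong for any endpoint whose effect has a sampling error near 31.6 raw units. The main prior is harmless for PASI and PLSS treatment effects. It can be material for thickness and LAG-3+ totals, and the effect on Ki67 is unknown. The direction for beta2 is usually, not always, toward no effect; for LAG-3+ % change it can go either way. All sizes are conditional on assumed SDs, baseline means and intercepts.

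This should be corrected before the table is used for decisions, but it does not touch the primary safety objective. The visit imbalance is real by schedule and secondary.

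**What to change.** 1. Set the prior precision of beta0, beta1, beta2 and mean_Base to 10^-6. At SD 150 the weight for beta2 is 10^6/(10^6 + 150²×0.1944) = 0.996 (6 v 9: 0.994). For mean_Base at SD 100 it is 10^6/(10^6 + 100²/21) = 0.9995. Alternatively, divide outcome and baseline by one common constant. Do not centre the baseline, because % change is beta2/mean_Base.
2. State the sensitivity prior for beta2 in outcome-SD units. A prior SD of one outcome SD keeps 1/(1 + 0.1944) = 84% pooled and 1/(1 + 0.2778) = 78% per dose, on every endpoint.
3. Keep the planned PASI/PLSS best score. Footnote that cohort 7 had no Day 85 assessment, or add a sensitivity run of the best score over Days 15, 29 and 43.

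The cost is SAP wording and a re-run. Items 1 and 2 give up nothing, and item 3 adds one footnote or one extra run.
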